Project title

Frail old patients with *Clostridioides difficile* infection: improvement of quality in treatment and care

Project manager **[name], Aarhus University Hospital**

Date: **June 26th, 2022**

Statistical considerations

Sample size calculation: 90-day mortality rate in CDI patients aged ≥ 70 years is 32% according to our cohort study (unpublished data) and another European study (1). Hence the 90-day mortality rate for the control group was set to 32%. The assumed effect of the intervention was calculated on the basis of the 12% 90-day mortality rate among CDI patients receiving FMT (2) and the 20% mortality rate in geriatric patients receiving CGA (3). However, in Hocquart's study (2) a sixth of the patients are below the age of 70 years and therefore, the 12% mortality rate might be underestimated. Furthermore, Hansen et al. (3) only performed CGA on moderate to severely frail patients. As we will include patients also with mild frailty, the 90-day mortality rate of 20% might be overestimated. Assuming an additive effect of CGA on FMT interventions, a mortality rate between 12 and 20% is realistic and estimated to be 15%, and therefore, a mortality difference of 32-15 = 17%. With a power of 80% and an alpha of 5%, 108 patients are needed in each group which is the final number of patients, not taking into account drop-outs.

Analyses of clinical treatment effect at 90 days of follow-up are divided into three parts: 1) intention-to-treat (ITT) analysis according to random allocation; 2) an as-treated analysis, taking cross-overs into account; 3) a per-protocol analysis including in the analysis only those patients who strictly adhered to the protocol. Differences will be examined with suitable statistics in relation to the distribution of data and data type. A statistical analysis plan will be performed before analysis of data. The statistical significance limit is 0.05. Subgroup analyses on primary and secondary efficacy measures are assessed for significance of sex, age, comorbidity, CDI number and number of FMT.

In interim analysis after inclusion of 60 patients, it is assessed whether the trial should be discontinued. Haybittle-Peto limits are used with a statistical significance level of 0.001. The analysis will be performed by an external reviewer.

References

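### Does the assumed 15% mortality contradict the plan's premise that CGA adds to the effect of FMT?

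*SAP*

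**What the plan says.** The point lies in the sample size calculation under Statistical considerations in the SAP. Control mortality comes from the sponsor's own cohort and a European study: "Hence the 90-day mortality rate for the control group was set to 32" per cent.

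The intervention rate starts from two literature figures: 12% at 90 days in CDI patients given FMT, and "the 20% mortality rate in geriatric patients receiving CGA". The SAP qualifies both. On the FMT study it says that "a sixth of the patients are below the age of 70 years and therefore, the 12% mortality rate might be underestimated". On the CGA study, which enrolled only moderately to severely frail patients, it says that "the 90-day mortality rate of 20% might be overestimated", because this trial also takes mildly frail patients.

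It then combines the two: "Assuming an additive effect of CGA on FMT interventions, a mortality rate between 12 and 20% is realistic and estimated to be 15" per cent. This gives "a mortality difference of 32-15 = 17" percentage points and, at 80% power and 5% alpha, 108 patients per group.

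**The concern.** An additive effect of CGA on top of FMT means that patients who receive both do better than patients who receive FMT alone. On any scale, combined mortality should then lie below the FMT-alone rate. The SAP instead places it between the FMT rate and the CGA rate, and the chosen 15% is above the cited FMT rate. At the upper end of the stated range, 20%, FMT would add nothing to CGA.

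The age caveat on the 12% might be thought to close the gap, but it is hard to make it do so. If a sixth of the FMT patients were under 70 and none of them died, the rate at 70 and over would be 12% / (5/6) = 14.4%, which is still under 15%. Taken at face value, the planning figure then gives CGA no credit.

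The 17-point difference is the only effect-size input to the 108 per group. If it were wrong in the unfavourable direction, or if the number did not follow from the stated rates, the size of the trial would be in question.

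**Working it through.** **Inputs, all from the sample size paragraph.** Control 32%; intervention 15%; power 80%; alpha 5%; equal groups. The SAP does not say whether alpha is one- or two-sided. Two-sided is assumed here because it reproduces the stated number.

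**1. The SAP's own figure.** With p1 = 0.32, p2 = 0.15, d = 0.17 and mean p = 0.235:

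- n = [1.96 × √(2 × 0.235 × 0.765) + 0.8416 × √(0.32 × 0.68 + 0.15 × 0.85)]² / 0.17²
- = [1.1753 + 0.4944]² / 0.0289 = 96.5 uncorrected
- With continuity correction: (96.5 / 4) × [1 + √(1 + 4 / (96.5 × 0.17))]² = 107.9, rounded up to 108

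The 108 per group is reproduced. Exact power at that size is 80.6%.

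**2. What literal additivity would give.** If both rates are read against the same 32%, FMT saves 32 − 12 = 20 points and CGA saves 32 − 20 = 12 points. Together they save 32 points, which puts combined mortality at 0%. Starting from 14.4% gives 14.4 − 12 = 2.4%. Neither is a credible planning value for frail old patients. The subtraction for CGA is also unsound, because the 20% comes from geriatric patients and not from CDI patients. The premise cannot have generated the number, and taking it literally would not improve the number.

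**3. Which way the mismatch points.** Number per group against 32%, same formula with continuity correction:

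| Intervention mortality | Per group |
|---|---|
| 12% (cited FMT rate) | 76 |
| 14.4% | 101 |
| 15% (SAP) | 108 |

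Any combined rate below the FMT rate would need fewer than 108. The SAP has chosen a larger trial than its premise implies.

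**4. What acting on the premise would cost.** Suppose the size were cut to 76 and true mortality were 15%. By the uncorrected normal approximation, z = (√76 × 0.17 − 1.1753) / 0.5874 = (1.4820 − 1.1753) / 0.5874 = 0.52, so power is about 70%. The same approximation gives 84% at 108.

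**5. How firm the 14.4% is.** It is not a figure in the SAP, which names the age problem but computes no correction. The sixth is stated for the study's patients, whereas the 12% is stated for those who received FMT. If the share under 70 among FMT recipients were a fifth, the bound would be 12 / 0.8 = 15.0%; if a quarter, 12 / 0.75 = 16.0%. Removing patients under 70 also does nothing to carry the rate over to a population selected for frailty. FMT-alone mortality in this trial could exceed 15%, so it is not shown that the plan gives CGA no credit.

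**The case for a change.** The best case for a change is that a sample size justification should let a reader get from premise to number, and this one does not. Neither stated caveat turns 15% into a joint effect: the age caveat raises the FMT rate by an unstated amount, and the frailty caveat only lowers the CGA rate. The SAP never calls 15% a cautious choice. The repair would be a single sentence, keeping 15% and 108 and describing 15% as a planning value set between the two cited rates.

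The criticism of the wording stands: the sentence claims additivity and then interpolates. The case for requiring a correction does not stand. A reader can see the two source rates, the doubts about each, the chosen value and the resulting difference, and can judge 15% on its merits. The proposed sentence would leave every planning input, the number of patients, the analyses and the conclusions unchanged.

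The other route is to derive a joint effect from each source study against its own controls and recompute. That would give a more optimistic effect and a smaller trial. Reasonable statisticians would dispute that trade, given how poorly both source populations match this one.

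**Conclusion.** The inconsistency is real but confined to the wording. The text claims an additive effect, and 15% is in fact a compromise between 12% and 20%. The calculation uses only 32% and 15%, and 108 per group is correct for them under a two-sided 5% test with continuity correction and 80% power. Relative to the stated premise the choice is cautious: even the cited FMT rate alone would need 76 per group, 32 fewer than planned.

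Cautious here means relative to an additive effect, not across the whole stated range. If true mortality were 20%, power at 108 per group would be about 52% (uncorrected normal approximation). That follows from choosing one value in an uncertain range, and rewording the premise would not alter it.

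Setting a planning value above an optimistic literature rate, with the doubts about that rate disclosed, is ordinary judgement. No change to the plan is needed.

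### The 108 per group assumes no cross-over, yet the plan provides for cross-overs only through an as-treated analysis and names none of its three analyses as deciding

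*SAP*

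**What the plan says.** All of this stands in the SAP under Statistical considerations.

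- **Sizing.** For control mortality, "Hence the 90-day mortality rate for the control group was set to 32"%. For the intervention arm, "a mortality rate between 12 and 20% is realistic and estimated to be 15"%. The plan concludes: "therefore, a mortality difference of 32-15 = 17"%. With 80% power and 5% alpha, "108 patients are needed in each group which is the final number of patients, not taking into account drop-outs".
- **Analyses.** The 90-day analysis has three parts. The first two are "intention-to-treat (ITT) analysis according to random allocation; 2) an as-treated analysis, taking cross-overs into account", and the third is per-protocol. None is called primary, and no cross-over rate is given.
- **Test.** "Differences will be examined with suitable statistics in relation to the distribution of data and data type".
- **Later plan.** "A statistical analysis plan will be performed before analysis of data".
- **Covariates already in use.** "Subgroup analyses on primary and secondary efficacy measures are assessed for significance of sex, age, comorbidity", followed by CDI number and number of FMT.

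**The concern.** Sizing and analysis rest on different premises. The full 17-point difference is what ITT would estimate if every patient stayed on the allocated treatment. If some controls receive the intervention, the ITT difference shrinks even when every patient's vital status at day 90 is known. The plan's remark about drop-outs does not cover this.

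The plan's only response to cross-over is the as-treated analysis, which groups patients by what they received. Because no analysis is named as deciding, nothing in this document stops an as-treated result from being read as the trial's answer if ITT narrowly fails. At stake are the 80% power, which holds only under an unstated condition, and the protection that randomisation gives the main comparison.

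**Working it through.** **1. Reproduce 108.** Inputs from the SAP: p1 = 0.32, p2 = 0.15, alpha 0.05, power 0.80. Sidedness is not stated. It is taken as two-sided, because one-sided gives 76, or 88 with continuity correction.

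n = [1.96·√(2·0.235·0.765) + 0.8416·√(0.32·0.68 + 0.15·0.85)]² / 0.17² = (1.1753 + 0.4944)² / 0.0289 = 96.5

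Continuity-corrected: (96.5/4)·[1 + √(1 + 4/(96.5·0.17))]² = 107.9, so 108. The stated figure reproduces exactly.

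**2. Dilute the ITT difference.** Let a share x of controls cross and take the intervention arm's mortality (full benefit, an assumption). The control rate becomes 0.32 − 0.17x and the intervention rate stays at 0.15. The plan gives no x, so a range is shown. Power is at 108 per group. The exact columns come from full binomial enumeration. The corrected chi-square and Fisher tests agree to the digits shown.

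| Controls crossing | Control rate | Uncorrected, normal formula | Uncorrected, exact | Corrected or Fisher, exact |
|---|---|---|---|---|
| 0% | 32.0% | 84.3% | 85.1% | 80.6% |
| 5% | 31.15% | 80.9% | 81.7% | 76.7% |
| 10% | 30.3% | 77.0% | 77.9% | 72.3% |
| 20% | 28.6% | 68.0% | 68.9% | 62.4% |

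If both arms cross equally, exact uncorrected power is 76.8% at 5% and 66.5% at 10%.

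**3. Limit for 80% power, one-way, uncorrected test.**
- Full benefit: x = 6.2% (formula) or 7.3% (exact). Since 0.062·108 = 6.7 and 0.073·108 = 7.9, this is 6 or 7 patients.
- Crossers reach only 20% mortality, the top of the plan's own range. They gain 12 of 17 points, so the limit is multiplied by 17/12, giving about 9-10%.
- Half benefit (0.32 − 0.085x): the limit doubles to 12.3% (formula) or 14.6% (exact). Power at 10% crossing is then 81.7%.

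**4. As-treated comparison with no true effect.** Let mortality be 32% in both arms, with a share c of controls crossing and mortality r among crossers (c and r assumed).

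Mortality in controls who stay = (0.32 − c·r)/(1 − c). Mortality in all treated = (0.32 + c·r)/(1 + c).

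- c = 0.20, r = 0.16: 0.288/0.80 = 36.0% versus 0.352/1.20 = 29.3%, a spurious benefit of 6.7 points.
- c = 0.20, r = 0.48: 0.224/0.80 = 28.0% versus 0.416/1.20 = 34.7%, a spurious harm of 6.7 points.
- c = 0.10, same values of r: benefit or harm of 3.2 points.

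Simulated trials of 108 per group with no effect give the matching error rates at 20% crossing:
- Crossers drawn at random from controls still alive: as-treated rejects in 6.8%, 13.5% and 28.3% of trials when 25%, 50% and 75% of deaths come before crossing.
- Sicker controls cross (twice the odds of later death, assumed): rejection is about 5.5-5.9% with 50% of deaths earlier. With 25% earlier, the apparent difference is −2.2 points, against the intervention.
- ITT rejects in 5.0-5.2%.

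**5. What covariate adjustment recovers.** In simulated trials with 10% full-benefit crossing and one baseline covariate of AUC 0.64, 0.70 or 0.74 (assumed), the adjusted ITT risk difference has power of 79%, 82% and 84%. The unadjusted test has about 77-78%. Type I error of the adjusted analysis is 4.9-5.2%.

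**The case against.** Several counter-arguments stand and limit the point.

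- **The plan provides for cross-overs but forecasts none.** A reader might infer that the trial expects them and is therefore underpowered. The document does not support that. Listing an as-treated analysis is a provision, and likely frequency commonly sits in the protocol, which is not at hand.
- **The corrected test's limit is not informative.** A reader might infer that under a continuity-corrected or Fisher test the trial fails once 0.8% of controls cross. The arithmetic is right, but it only reflects a design sized to just 80%, where almost any departure falls below the target. The document fixes no test.
- **Full benefit is a worst case for one-way crossing.** The 15% assumes that CGA adds to FMT. A control who gets one component, or gets it late, need not gain all 17 points. If the 32% already includes some use of the intervention, part of the dilution is covered. The document does not say.
- **The plan's own uncertainty is larger.** Across its 12-20% range for the intervention arm, exact uncorrected power at 108 runs from 95% to 53%. Losing 3 or 7 points at 5% or 10% crossing is small beside that.
- **As-treated bias has no fixed direction.** A reader might infer that reclassifying crossers must favour the intervention, because a control has to be alive to cross. That holds if crossers are otherwise typical survivors. If sicker controls cross, the bias can vanish or reverse.
- **A later plan is promised.** It can name the test and the deciding analysis.

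None of this removes the mismatch. The undiluted sizing is set in this document, the three analyses are unranked, and one of them is not a randomised comparison.

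**Conclusion.** The point holds as a conditional one. The 108 is right for 32% versus 15%, and no loss of power is demonstrated. What the document leaves open is that its 80% assumes little or no cross-over while its analysis section makes room for it. Under an uncorrected test, the room is about 6-7% of controls crossing with full benefit and about 14% with half benefit. Equal crossing in both directions leaves less, about 3% per arm (2.7% by formula) with full effect.

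The firmer part concerns the ranking of analyses. With no true effect and 20% crossing, the as-treated difference ranges from 6.7 points of benefit to 6.7 points of harm for the assumed crosser mortalities. It cannot substitute for ITT in either direction. These sizes depend on assumed cross-over rates, timing of deaths and selection of crossers, none of which the document gives. The change is worth making because it costs almost nothing.

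**What to change.** Change text only:

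1. State that the ITT comparison of 90-day mortality decides, and that the as-treated and per-protocol analyses are supportive and cannot replace it.
2. Before any outcome by arm is seen, including at the interim analysis after 60 patients, specify the ITT analysis as a risk difference with 95% CI, adjusted for baseline age and comorbidity. The plan already uses both variables for subgroups. Adjustment recovers some of the power lost to dilution, by an amount that depends on how prognostic they are.
3. Beside 108, state that 80% power assumes little or no cross-over. Give the limit as a range: about 6-7% of controls with full benefit and about 14% with half, uncorrected test. Report the observed cross-over rate beside the ITT interval.

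Cost: no extra patients. Age and comorbidity must be recorded at entry. The wording can go into the analysis plan that the SAP already promises, provided it is fixed before the interim look.

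### Must the 60 patients at the interim analysis have reached 90 days, and does it matter that the SAP does not say so?

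*SAP*

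**What the plan says.** All the relevant text is under Statistical considerations in the SAP.

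- The interim paragraph sets the milestone: "In interim analysis after inclusion of 60 patients, it is assessed whether the trial should be discontinued". It then gives the limit, "Haybittle-Peto limits are used with a statistical significance level of 0.001", and the analyst: "The analysis will be performed by an external reviewer".
- The analysis paragraph ties the treatment effect to a fixed follow-up time: "Analyses of clinical treatment effect at 90 days of follow-up are divided into three parts". It leaves the test open: "Differences will be examined with suitable statistics in relation to the distribution of data and data type". It also says that a statistical analysis plan is still to be made before the data are analysed.
- The sample size paragraph rests on 90-day mortality of 32% in controls and 15% with the intervention, and concludes "With a power of 80% and an alpha of 5%, 108 patients are needed in each group".

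No sentence gives a follow-up condition or data cut-off for the 60 patients, and none names the interim endpoint.

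**The concern.** Inclusion is an entry event, whereas the outcome that sizes the trial takes 90 days to observe. The milestone therefore fits two looks, up to 90 days apart. In one, the external reviewer waits until each of the first 60 has died or reached 90 days. In the other, the data are cut when the 60th patient enters, and those who entered in the preceding 90 days and are alive have incomplete follow-up.

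The second look does not suit a simple 90-day proportion. Restricting to completers discards patients, and counting pending patients as alive records later deaths as survivals. With fast accrual, few or none of the 60 would have a complete outcome. If the choice were made only when the data are cut, the stopping assessment would not be fully fixed in advance. What could be at stake is the chance of stopping early, the risk of stopping falsely, and the validity of the final test.

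**Working it through.** **Inputs from the SAP:** 32% versus 15% mortality at 90 days, 80% power, 5% alpha, 108 per group (216 in total), interim at 60, limit 0.001.

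**Inputs assumed:** the interim compares 90-day mortality, the 0.001 is two-sided, and the split is 30/30. For a cut at the 60th entry, accrual and the timing of deaths within 90 days are also assumed.

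**1. The plan's sample size.** The mean rate is (0.32 + 0.15)/2 = 0.235. Without a continuity correction,

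n = [1.960·√(2·0.235·0.765) + 0.842·√(0.32·0.68 + 0.15·0.85)]² / 0.17² = (1.175 + 0.494)² / 0.0289 = 96.5.

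With the correction,

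n = (96.5/4)·[1 + √(1 + 4/(96.5·0.17))]² = 107.9, so 108 per group.

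The stated figure reproduces as a two-sided, continuity-corrected calculation.

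**2. The look with all 60 complete.** Expected deaths are 30·0.32 = 9.6 and 30·0.15 = 4.5, or 14.1 in total. The limit requires |z| > 3.29. The smallest splits that cross are:

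- 10 v 0: z = 3.46; Fisher p = 0.0008
- 12 v 1 by Pearson (z = 3.45), 13 v 1 by Fisher (p = 0.0004)
- 14 v 2: z = 3.50; Fisher p = 0.0009

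The chance of crossing is the sum, over all crossing pairs, of the two binomial probabilities multiplied together:

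| True rates | Pearson | Fisher |
|---|---|---|
| 32% v 15% | 2.63% | 1.91% |
| 23.5% in both arms | 0.054% | 0.034% |

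**3. A cut at the 60th entry (illustrative).** If 216 patients enter evenly, about 216·90/(accrual in days) arrive in any 90 days, and 60 minus that number have full follow-up. For 24 months this is 216·90/730 = 26.6, leaving 33.4. Simulation used two death-time shapes within 90 days, constant hazard and front-loaded, with 40,000 trials for log-rank and 100,000 for Pearson. The last three columns give the chance of crossing 0.001 under 32% versus 15%.

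| Accrual | Complete at cut | Log-rank, censored | Completers only, Pearson | Pending counted alive, Pearson |
|---|---|---|---|---|
| 18 months | about 24 | 1.3–1.5% | 0.3% | 0.9–1.2% |
| 24 months | about 33 | 1.6–1.8% | 0.8% | 1.2–1.5% |
| 36 months | about 42 | 2.0–2.1% | 1.4–1.5% | 1.6–1.8% |
| 48 months | 46–47 | 2.2–2.4% | 1.6–1.7% | 1.8–2.0% |

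The log-rank test with all 60 complete crosses in 2.7–3.0%. At the cut, 10.0 to 12.9 of the 14.1 expected deaths are already known. With no effect, every version crosses in 0.02–0.08%. Outside this range, 12 months of accrual would leave about 7 complete (60 − 216·90/365 = 6.7). With 6 months there would be none, since the 60th patient enters on about day 50.

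**4. Overall type I error.** With all 60 evaluable, the information fraction is 60/216 = 0.278, so the interim and final statistics correlate at √0.278 = 0.53. Testing at 0.001 and then at 0.05 gives an overall two-sided error of about 0.0505.

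**5. Cost of waiting.** If inclusion continues, a look 90 days later lets about 35 (18 months) to 13 (48 months) more patients enter first.

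**The case for a change.** The best argument for a change is that the SAP itself sets the milestone, the limit and the analyst, so the loose end cannot simply be assigned to a protocol that is not shown. The person who must interpret the sentence is outside the trial team, and the sentence about a later analysis plan mentions neither the interim nor a cut-off. One clause would close the gap at no cost beyond wording. Under fast accrual, a literal cut with a simple proportion would have almost nothing to analyse.

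Much of this stands. The gap is real, and a clause would do no harm. What does not follow is that the plan is wrong. No figure is incorrect and no two passages conflict. The natural reading, 90-day status in the first 60, agrees with the rest of the document. The other reading is also valid if handled by a censored comparison. Either clause would be acceptable, so the choice is one of preference. The open choice of test belongs to the paragraph on the 90-day analyses and is a separate matter. The poorest handling, a completers-only proportion, costs some of an already small chance of stopping and does not raise false stopping above 0.1%.

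**Conclusion.** No change follows. The follow-up condition is an unstated detail that a competent external reviewer would settle sensibly, and sound conclusions do not depend on how it is settled. With 30 complete per arm, the look stops in about 2 to 3% of trials under the design effect and in fewer than 0.1% with no effect. What limits it is the strict limit combined with about 14 expected deaths, rather than the cut-off date. Overall type I error stays at about 0.05.

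These figures assume a 90-day mortality endpoint at the interim, a two-sided 0.001 and a 30/30 split. The contrast between the two looks, for example 1.3% against 2.7% by log-rank at 18 months, also rests on assumed accrual and death times. It is a scenario and should not be read as a property of this plan.
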